6.3.8 Adverse Events

AEs will be coded according to the Medical Dictionary for Regulatory Activities (MedDRA) system.

The severity of adverse events will be given in grades 1 to 5 per National Cancer Institute common terminology criteria for adverse events (CTCAE) version 4.0.

All AEs were categorized by the Investigator with respect to their possible relationship to the IMP. The relationship of the AE to AG019, as well as the relationship of the AE to teplizumab, will be assessed separately by the investigator to be not related, unlikely, possible, probable or definite. The categorization:

- reasonably related defined as possible, probable or definite versus
- not reasonably related defined as not related or unlikely will be given in summaries of all adverse events.

If a subject has more than one event with the same preferred term (PT), then the worst severity and the worst relationship will be used.

A TEAE is defined as any adverse event (AE) not present prior to the initiation of the treatment(s) or any AE already present that worsens in either intensity or frequency following exposure to the treatment(s). Hence, events with an onset time at or after the time of treatment start are treatment emergent. Events present at baseline that worsen during the study in either intensity or frequency are also treatment emergent, whereas events present at baseline that become less severe during the study are not. Events that recur during the study are treatment emergent if they recur after complete or partial recovery of the initial event, i.e. should the event first become less severe and then return to its initial severity, it will be considered as a TEAE. AEs reported on the same day as treatment start or after treatment start will be considered TEAEs, as investigators are instructed only to report TEAEs after treatment start.

A Serious Adverse Event (SAE) is defined as any AE occurring at any dose regardless of relationship to IMP that results in any of the following outcomes:

- results in death,
- is life-threatening,
- requires inpatient hospitalisation or prolongation of existing hospitalisation,
- results in persistent or significant disability/incapacity, or
- is a congenital anomaly/birth defect.

If the start date of an AE is missing, it will be assumed that the AE started after the first administration of IMP. If the start date of an AE is partially missing, and it has started the same year and/or month as the IMP it will be assumed that the AE started after the first administration of IMP. If an AE occurred on the same day as dosing but the onset time is missing the AE will be assumed to be a TEAE.

The infusion of teplizumab was considered withheld if the answer to the CRF question 'Was the Teplizumab infusion given?' was 'No, infusion not started' and/or if the answer on the AE page on 'Action Taken With Study Treatment Teplizumab' was 'Drug interrupted' or 'Drug withdrawn'.

Study treatment of AG019 was considered discontinued if the answer to the CRF question "Action Taken with Study Treatment AG019" was "Drug interrupted" or "Drug withdrawn".

A summary table per cohort will present number of TEAEs, number of unique TEAEs (counted once within each subject at the preferred term level) and number of subjects with at least one event for TEAEs, SAEs, related TEAEs, TEAEs leading to discontinuation of IMP/withdrawal and more.

Tables with

- All AEs by System Organ Class (SOC) and PT,
- All TEAEs by SOC and PT, in total and for the AG019 treatment period only,
- All TEAEs by SOC and PT according to severity, in total and for the AG019 treatment period only,
- All TEAEs by SOC and PT according to relatedness, in total and for the AG019 treatment period only,
- All serious TEAEs by SOC and PT,

will be given. If there are no events an empty table will be produced.

All AEs will be listed. In addition all TEAEs leading to AG019 treatment discontinuation and study infusion withholding will be listed.

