8.1. Adverse Event Definition

An adverse event (AE) is any untoward medical occurrence in a patient administered an investigational product or in whom an investigational product is to be administered, and which does not necessarily have a causal relationship with this treatment. An AE can be any unfavorable and unintended sign (e.g. an abnormal laboratory finding), symptom or disease temporally associated with the use of an investigational product, whether or not considered related to this investigational product. This includes an event that emerges during treatment having been absent pre-treatment or an event that worsens relative to the pre-treatment state ("treatment-emergent adverse event" [TEAE]). Recurrent symptoms of a chronic pre-existing condition are not considered AEs unless they occur in a worse or unexpected pattern during study drug administration.

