After all patients in all AG019 and Combination cohorts have completed their 6-month follow-up visit unblinding will be done and all data will be analyzed and reported. After completion of the full 12 months follow-up all additional data will be analyzed and reported separately.

More details on the analysis and presentation of study results will be provided in the statistical analysis plan (SAP). The SAP will be finalized prior to the unblinding of treatment allocation codes.

10.1.Study Endpoints

Primary Endpoint

The primary end point will be assessed by analysis of the incidence of treatment-emergent adverse events (TEAEs) collected up to the 6-month follow-up visit. A TEAE is defined as any event not present prior to the initiation of the treatment(s) or any event already present that worsens in either intensity or frequency following exposure to the treatment(s).

Secondary Endpoints

The pharmacodynamic activity of the study drug(s) will be assessed by measurement of biomarkers in blood and serum samples. Relevant parameters will be assessed, including immune markers for effect, relevant T1D parameters and relevant cytokines. Details about the analysis of the collected PD samples will be described in the SAP.

Following parameters will be assessed for analysis of systemic and local exposure to *L. lactis*:

- Presence of live L. lactis clinical strain bacteria in whole blood
- Measurable serum levels of hIL-10 and hPINS
- Presence of *L. lactis* clinical strain bacteria in fecal excretion

Safety information collected at all other time points will be assessed as secondary end points.

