3 EFFICACY AND SAFETY ENDPOINTS

3.1 Primary Endpoint

The primary endpoint will be assessed by analysis of the incidence of treatment-emergent adverse events (TEAEs) collected up to the 6-month follow-up visit. A TEAE is defined as any adverse event (AE) not present prior to the initiation of the treatment(s) or any AE already present that worsens in either intensity or frequency following exposure to the treatment(s).

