6.1 Changes in the Planned Analyses

There has been no changes to the planned analyses.

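### SAP 6.3.8 counts a pre-existing event that partly improves and only returns to its initial severity as a TEAE, which is wider than the protocol's definition and is not declared as a change

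*SAP*

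**What the plan says.** - **Primary endpoint (SAP 3.1; Protocol 10.1 matches).** "The primary endpoint will be assessed by analysis of the incidence of treatment-emergent adverse events (TEAEs) collected up to the 6-month follow-up visit".
- **Definition for events that already exist.** Protocol 10.1 admits "any event already present that worsens in either intensity or frequency following exposure to the treatment(s"). SAP 3.1, 6.3.1 and 6.3.8 repeat this almost word for word. None of them names the level against which worsening is measured.
- **Comparator.** Protocol 8.1 does name one. Besides events that newly appear on treatment, it includes "an event that worsens relative to the pre-treatment state". It adds: "Recurrent symptoms of a chronic pre-existing condition are not considered AEs unless they occur in a worse or unexpected pattern during study drug administration".
- **Recurrence rule (SAP 6.3.8).** The SAP first says that baseline events which become less severe are not treatment-emergent. It then states: "Events that recur during the study are treatment emergent if they recur after complete or partial recovery of the initial event", and explains that "should the event first become less severe and then return to its initial severity, it will be considered as a TEAE".
- **Reporting rule (SAP 6.3.8, next sentence).** Any AE reported on the day treatment starts, or later, is taken as a TEAE.
- **Declared changes (SAP 6.1).** "There has been no changes to the planned analyses".

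**The concern.** The recurrence sentence opens a route to TEAE status that the protocol does not have. A complaint present before the first dose, eased on study and then back at its old level, has not exceeded its pre-treatment state at any time. The SAP nevertheless counts it as treatment-emergent. Because partial recovery is enough, the complaint need never have stopped.

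TEAE incidence is the primary endpoint, and descriptive tables are the study's main output. If the derivation follows the SAP sentence, the TEAE tables (overall, by severity and by relationship to AG019) can include events that do not meet Protocol 8.1. A reader of the study report would not know this, because no departure is declared.

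**Working it through.** The documents give no TEAE rate, power or calculated sample size to reproduce, so the check is mainly a comparison of texts.

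**Step 1. One test course under each text.** Take grade 2 before first dose, grade 1 on treatment, then grade 2 again. The worst post-dose grade is max(1, 2) = 2, which does not exceed 2.

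| Text | Comparator | Result |
|---|---|---|
| Protocol 8.1 | state before treatment | not a TEAE |
| Protocol 10.1, SAP 3.1 | none named; must worsen | not a TEAE against the pre-treatment level; arguable against the on-treatment low |
| SAP 6.3.8 recurrence sentence | return to initial severity after a dip | TEAE |

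**Step 2. Where the rule decides anything.**
- Event began on or after first dose: already a TEAE by onset. Only the event count can change.
- Event began before first dose and later exceeds its earlier level: a TEAE under every text.
- Event began before first dose, resolved fully, then restarted: reasonably a new event.
- Event began before first dose, eased only in part, then returned to its initial level: a TEAE only through the recurrence sentence. This is the case in dispute.

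**Step 3. Which events can fall in the last group.** Protocol 8 puts conditions existing before screening into medical history and records AEs from consent. Screening takes place within 28 days before first administration (Protocol 4). The group is therefore mainly AEs that arise between consent and first dose.

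**Step 4. Interaction with the reporting rule.** If the return is reported as an AE on or after Day 1, the next sentence of SAP 6.3.8 already makes it a TEAE. Removing the recurrence wording alone would leave such events counted.

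**Step 5. Size for one patient.** Each combination cohort has 10 × 4/5 + 2 = 10 active patients and 10 × 1/5 = 2 placebo patients (Protocol 3.3). Each AG019 cohort has 4 to 6 repeat dose patients. One patient whose only TEAE arises through this rule shifts subject-level incidence by 1/n:
- n = 2: 50 points
- n = 4: 25 points
- n = 6: 16.7 points
- n = 10: 10 points

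If the patient has another TEAE, subject-level incidence does not move. The number of TEAEs can still change. The preferred-term count can change if the patient has no other TEAE of that term.

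**Step 6. Chance of at least one such patient.** The documents give no rate. Let q be the assumed proportion of patients who would count only through this rule, so that P = 1 − (1 − q)^n:

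| n | q = 2% | q = 10% |
|---|---|---|
| 2 | 4% | 19% |
| 4 | 8% | 34% |
| 10 | 18% | 65% |

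These values of q are illustrative and have no source in the documents.

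**The case against.** **The endpoint definition names no comparator.** A reader might infer that SAP 6.3.8 flatly contradicts the primary endpoint's own definition. It does not quite. A rebound from an improved level can be called a worsening after exposure, and Protocol 10 leaves analysis detail to the SAP. Recurrence after full recovery can also be read as increased frequency. The clear conflict is with Protocol 8.1. What stands against the SAP is that neither argument fits well with partial recovery followed by a return to the old level, once worsening is judged as Protocol 8.1 says.

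**Fluctuating chronic complaints are mostly kept out upstream.** A reader might infer that ordinary ups and downs of long-standing conditions will flood the tables. Medical history recording and the Protocol 8.1 rule on chronic conditions prevent most of that. This objection stands and narrows the point to events that start between consent and first dose.

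**Visit frequency.** A reader might infer bias from the daily visits on Days 1 to 12 in the combination cohorts. Active and placebo patients in a cohort follow the same schedule, so visit frequency does not favour either arm. All patients other than single dose patients keep an electronic diary from consent to study end (Protocol 6.4.1), so capture does not rest on visits alone. More contacts than in the AG019 cohorts might record more dips and returns, but no figure supports this.

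**Direction and consequence.** Over-counting is the cautious direction in a first-in-human safety study. There are no hypothesis tests, and all AEs are tabulated and listed in any case. This also stands. It limits the importance of the point but does not settle which definition the primary tables follow.

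**Conclusion.** The mismatch is real. SAP 6.3.8 classifies as treatment-emergent a pre-existing event that only regains its initial severity after partial improvement. Protocol 8.1 would not, and the primary-endpoint definition asks for worsening. SAP 6.1 declares no change.

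The likely effect is a modest over-count of TEAEs and preferred terms. The shifts of 10 to 50 points in subject-level incidence are what one reclassified patient with no other TEAE would cause in the planned groups. They are not estimates of the expected effect, and the same 1/n would apply to any misclassified patient. The documents do not show how often such courses occur, and they do not support a claim of bias between active and placebo.

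The conclusion rests on two readings: that Protocol 8.1 supplies the comparator that Protocol 10.1 and SAP 3.1 leave out, and that the recurrence sentence covers baseline events. The second is the natural reading, because the sentence before it concerns events present at baseline. The correction should be made because it is cheap and aligns the primary derivation with the protocol.

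**What to change.** In SAP 6.3.8, drop the mention of partial recovery and the explanatory clause on returning to initial severity. Put in their place:

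> An event present before first IMP is a TEAE only if its severity grade or frequency after first IMP exceeds the worst pre-treatment level. An event that has fully resolved and starts again after first IMP is a new TEAE, subject to the Protocol 8.1 rule on chronic conditions. This rule takes precedence over the sentence that treats every AE reported from the day of treatment start as a TEAE.

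The precedence statement is essential. Without it, a return to the old level that is reported after dosing would still be counted. For the same reason, a return entered as a new record should not become a TEAE merely through its new onset date unless the earlier event had fully resolved.

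If the sponsor prefers the broader rule, declare it in SAP 6.1 and show these events separately from TEAEs that meet the protocol definition.

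The cost is a few sentences and the matching derivation. TEAE counts may be slightly lower. No safety data are lost, because the table and listing of all AEs still show the excluded events.

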7.3. Repeat Dose Patients

7.3.1Screening Visit (Day -28 – Day 0)

Following screening observations and procedures will be completed within 28 days prior to randomization:

- Signed and dated ICF
- Assessment against inclusion and exclusion criteria
- Medical history
- Demographic Data
- Physical Exam
- Vital signs
- 12-lead ECG
- Serum pregnancy test (in females of childbearing potential)
- Blood sampling for local lab (hematology, full chemistry, specific screening blood analysis, infectious disease, autoantibodies)
- SARS-Cov2 PCR test (only applicable for patients in the combination cohorts)
- Blood sampling for mechanistic assessments (only for repeat dose patients in AG019 Cohorts
 2 and 4 and for patients in the combination cohorts)
- Blood sampling for central lab (HbA1c)
- Blood sample for central lab PK
- Feces collection for central lab PK¹⁰ (only for repeat dose patients in AG019 Cohorts 2 and 4 and for patients in the combination cohorts)
- Tuberculosis test
- Mixed Meal Tolerance Test (MMTT) for C-peptide and glucose assessments
- Drugs of abuse test
- Record concomitant medications
- Record adverse events
- ePRO preparation / explanation
- Assessment of insulin use and hypoglycemic events
- Register patient in IRT
 - Registration in IRT should be done as soon as eligibility is confirmed and ICF is signed to allow for timely shipment of study drug. Ideally this should be done at least 1 week before the Day 1 visit (start of treatment visit).

7.3.2Baseline Visit (Day 1 – start of active treatment)

Prior to the first administration of IMP, following observations and procedures will be completed:

Confidentiality Statement

This document contains confidential information. It is intended solely for the use of the principal investigator, coinvestigators, staff, appropriate institutional review boards or ethical committees, and other required regulatory bodies.

AG019-T1D-101 CSP Final 9.0 11-Jun-2020

¹⁰ Sites should make every reasonable effort to collect feces during the screening visit. If feces cannot be collected during the screening visit, patients will be asked to collect feces between the Screening visit and the Day 1 visit, according to the instructions provided by the site and the collection materials provided by the central lab.

- SARS-Cov2 PCR test (only applicable for patients in the combination cohorts, to be taken within
 3 days before the first teplizumab/placebo infusion)
- Register visit in IRT
- Physical Exam
- Vital Signs

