8. ADVERSE EVENT REPORTING

Throughout the study, AEs will be recorded in the source documents and transcribed onto the appropriate pages of the eCRF regardless of whether the AEs are considered treatment related. All AEs with onset dates from signature of the ICF through study exit will be recorded as an AE on the eCRF. All SAEs with onset dates from signature of the ICF through study exit must be recorded following the guidelines in Sections 8.4, 8.6, 8.7, 8.8 and 8.9. Any AE that occurs at any time after completion of the study, which the investigator considers to be related to study drug, must be reported.

Conditions existing prior to screening will be recorded as part of the patient's medical history. To avoid confusion, the AE should be recorded in standard medical terminology. The Investigator is responsible for assessing the relationship of AEs to the AG019 as well as to teplizumab (Section 8.3).

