8.4. Recording of Adverse Events

All AEs encountered during the clinical study will be recorded in detail in the source documents and documented in the eCRF, from signature of the ICF through study exit. All AEs that meet the seriousness criteria (Section 8.6) should also be recorded on the SAE Report Form. All SAEs must be reported to the sponsor or delegated organization within the timeline stated in Section 8.7.

The recording of AEs will be based on data obtained from the following sources:

- Medical and surgical history
- Physical examinations including vital signs
- Clinical laboratory test results
- Information provided by the patient, either during the follow-up visits or in the patient's diary All clinical events, including both observed (such as any reaction at sites of application) and volunteered problems, complaints, or symptoms, are to be recorded. The need to capture this information is not dependent upon whether the clinical event is associated with the use of any IMP.

If at any time during the study a patient develops symptoms suggesting clinically significant bacteremia that can be attributed to *L. lactis* sAGX0407 (as determined by three consecutive positive blood cultures), study treatment will be discontinued.

A disposition plan for the management of clinical sepsis is provided in Appendix B.

Confidentiality Statement

For the purposes of this study, hypoglycemia events classified as level 1 as defined in Section 8.2.1 will not be recorded separately on the hypoglycemia event eCRF, unless the investigator feels that the event is medically important. Hypoglycemia events level 2 and 3 as defined in Section 8.2.1 will be recorded separately on the hypoglycemia event eCRF. The evaluation that produced the value or result should be repeated until that value or result returns to normal or can be explained and the participant's safety is not at risk. In addition, all hypoglycemia events meeting the definition of SAE as mentioned in Section 8.6, should be recorded as serious adverse events in the eCRF.

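### SAP 6.3.8 gives two incompatible rules for a treatment-emergent AE, and one of them counts Day 1 events known to have begun before the first dose

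*SAP*

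**What the plan says.** SAP 3.1 bases the primary endpoint on "analysis of the incidence of treatment-emergent adverse events (TEAEs) collected up to the 6-month follow-up visit". SAP 3.1, 6.3.1 and 6.3.8, and Protocol 10.1, share one definition: the event was absent before treatment began, or was present and then worsened in intensity or frequency.

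SAP 6.3.8 turns this into working rules:

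- **Onset rule:** "events with an onset time at or after the time of treatment start are treatment emergent". Baseline events count only if they worsen or recur.
- **Reporting rule, same paragraph:** "AEs reported on the same day as treatment start or after treatment start will be considered TEAEs", with the reason "as investigators are instructed only to report TEAEs after treatment start".
- **Missing-time rule, a little later:** "If an AE occurred on the same day as dosing but the onset time is missing", the event is assumed to be a TEAE.

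Protocol 8 sets the recording duty: "All AEs with onset dates from signature of the ICF through study exit will be recorded as an AE on the eCRF". Protocol 8.4 repeats it: AEs are "documented in the eCRF, from signature of the ICF through study exit". For the Day 1 visit of repeat dose patients, Protocol 7.3.2 opens its list with "Prior to the first administration of IMP, following observations and procedures will be completed", and recording AEs is on that list. Protocol 7.2.2 does the same for single dose patients.

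**The concern.** The onset rule and the reporting rule can classify the same event differently, and the SAP sets no order of precedence. The reason offered for the reporting rule conflicts with the protocol's recording duty.

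The schedule makes the conflict practical. AEs are to be recorded on Day 1 before dosing. Repeat dose patients also keep a diary from consent that includes AEs (Protocol 6.4.1), and it is reviewed at the Day 1 visit. Events that began before the first dose can therefore properly reach the eCRF on Day 1.

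At stake is the primary endpoint and every TEAE table built on it, in groups so small that one patient is visible. The Phase 1b cohorts have no placebo group against which over-counting could be seen.

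**Working it through.** The plan states no figure to reproduce: the study is descriptive, with no power calculation. The main check sets the rules side by side.

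**Step 1. Apply each rule to the same event.**

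| AE | Definition, onset and missing-time rules | Reporting rule, 'reported' = date of event | Reporting rule, 'reported' = date recorded |
|---|---|---|---|
| Began in screening, did not worsen or recur, recorded at Day 1 | Not a TEAE | Not a TEAE | TEAE |
| Began on Day 1 at a known time before dosing | Not a TEAE | TEAE | TEAE |
| Began on Day 1, time missing | TEAE | TEAE | TEAE |
| Began after dosing | TEAE | TEAE | TEAE |

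The second row is wrong under either meaning of 'reported'. The first row is wrong only under the recording-date meaning. The third row shows that the reporting rule leaves the missing-time rule with nothing to do: that rule is needed only if a known time would otherwise decide.

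**Step 2. Test the reason given.** Protocol 8 and 8.4 require all AEs between consent and study exit, without limiting them to TEAEs. No instruction of the kind the SAP cites appears in the protocol.

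**Step 3. Group sizes.** Single dose: 2 per AG019 cohort. Repeat dose: 4 to 6 per AG019 cohort. Each combination cohort has 2 open-label active patients plus 10 randomized 4:1, so active = 2 + 10 × 4/5 = 10 and placebo = 10 × 1/5 = 2.

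**Step 4. Effect of one misclassified patient.** If the patient has no other TEAE, incidence moves by 100/n points:

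- n = 2: 50
- n = 4: 25
- n = 6: 16.7
- n = 10: 10

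If the patient has a true TEAE as well, patient-level incidence does not move, but the event count still rises by one.

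**Step 5. How likely, under an assumption.** The documents give no rate of pre-dose AEs. Suppose a share q of patients, from 5% to 30%, has a pre-dose AE that the reporting rule would count. The chance of at least one such patient in a group is 1 − (1 − q)^n:

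| n | q = 5% | q = 30% |
|---|---|---|
| 2 | 9.8% | 51% |
| 4 | 18.5% | 76% |
| 6 | 26.5% | 88.2% |
| 10 | 40.1% | 97.2% |

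With true patient-level incidence p, and independence, the expected rise is (1 − p) × q. That is 2.5 to 15 points at p = 50% and 0.5 to 3 points at p = 90%. The upper values of q are more plausible under the recording-date meaning; under the event-date meaning only the pre-dose hours of Day 1 contribute.

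**The case against.** The strongest reply is that the SAP's own usage points to the date of the event. Its hypoglycemia periods (SAP 6.3.9) use 'reported' on the day of treatment start in contrast to events up to the day before. Relative day is computed from the start date, the missing-data rules work on start date and onset time, and the definition appears three times. On that reading events that began before Day 1 are excluded, and what remains is a matter of hours. This stands as far as it goes, but the Day 1 event with a known pre-dose onset is still misclassified.

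Other replies have some force:

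- The eCRF completion guidance is not among the documents, so an instruction there cannot be ruled out. It would, however, contradict Protocol 8 and 8.4.
- The Day 1 lists also include giving the first dose, so their pre-dose heading is not strictly literal. AE recording still comes before dosing in both lists.
- All AEs are tabulated and listed whatever their TEAE status, with date and relative day. That would expose a screening event, but relative Day 1 covers both sides of the first dose.

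Two stronger readings are tempting and not supported. A reader might infer that screening AEs do enter the primary endpoint. That needs 'reported' to mean the recording date and also to override the onset rule; the SAP says neither, so one can say only that they could enter. A reader might also infer that the over-count dilutes a difference between active and placebo. The rule applies to every group, SAP 6.4 and 6.5 plan no comparison or test, and nothing in the documents shows how often such events occur.

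**Conclusion.** The SAP is wrong as written. It holds two incompatible rules for classifying the events in the primary endpoint, and one rests on an instruction that the protocol contradicts. Whatever 'reported' means, that rule turns a Day 1 AE with a known pre-dose onset into a TEAE, against the definition in both documents.

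The error runs one way, towards over-counting, and no hypothesis test is affected. Its size per patient is that of Step 4, on the condition that the patient has no other TEAE. The overall expected shift cannot be fixed from the documents; the range in Step 5 depends on assumed rates and could be small if nearly every patient has a true TEAE. The case for correcting it rests on the contradiction itself and on groups of 2 to 10 patients, not on a demonstrated large bias.

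**What to change.** In SAP 6.3.8:

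1. Delete the sentence that makes TEAE status depend on reporting, together with its reason.
2. State that TEAE status is set by AE onset date and time against the first dose of IMP.
3. Count a Day 1 AE as treatment-emergent if onset is at or after dosing, or if the onset time is missing, as the SAP already provides.
4. Keep the existing rules for worsening, recurrence and missing or partial dates.

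The cost is one deleted sentence, one clarified sentence and a check that the TEAE program follows them. The CRF is not shown, but the SAP already refers to AE start date and onset time, so no new data collection seems to be needed; where a time is absent, the missing-time rule covers it. The change should be settled before the blind is broken for the third interim analysis, the point by which SAP 6.9 says decisions on blinded data are taken.
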